After consenting, subjects will be assigned a new screening number. Subjects who are found to be eligible will retain the same subject number they had been assigned in their previous trial. For purposes of ensuring subject safety, tolvaptan exposure of at least 18 months is required for all subjects. While Trial 156-13-210 remains blinded, subjects enrolling from any prior trial besides Trial 156-08-271 are scheduled to have monthly hepatic monitoring for the first 18 months of this trial. After that, following the approval of the medical monitor, hepatic monitoring will take place every 3 months. Subjects enrolling from Trial 156-08-271 will have hepatic monitoring every 3 months. All Trial 156-13-210 subjects who are eligible for this trial will initially be scheduled to have trial visits and hepatic monitoring monthly for the first 18 months, then every 3 months thereafter, because their tolvaptan exposure cannot be determined since Trial 156-13-210 is a double blind trial. Once unblinding occurs, it can be determined which subjects received tolvaptan in Trial 156-13-210. These subjects may have their trial visits/hepatic transaminase monitoring changed to every 3 months sooner as their previous tolvaptan exposure in Trial 156-13-210 can count towards the 18-month threshold. Subjects from prior tolvaptan trials other than Trial 156-08-271 will have monthly trial visits/ALT level assessments for the first 18 months. After that, the trial visits/ALT monitoring will be conducted every 3 months after the change in frequency is confirmed with the medical monitor.

Enrollment in this trial will be closed when the last eligible subject from Trial 156-13-210 enrolls in this trial.

The duration of this trial is planned to continue

- Until the last subject from Trial 156-13-210 completes 18 months of tolvaptan treatment in this trial
- Subjects enrolling from other trials will conclude their participation once tolvaptan becomes available through routine prescription or through a CCI Trial 156-13-210 subjects may opt to conclude their participation in this trial if tolvaptan becomes available before they complete 18 months of treatment in this trial

Protocol 156-13-211

[figure not shown]

Figure 3.1-1 Trial Design Schematic

Protocol 156-13-211

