2. CCI [REDACTED]
3. Record vital signs (post-void weight, seated heart rate, and calibrated blood pressure measurement).
4. Collect blood for central laboratory assessments for serum sodium, serum creatinine, and ALT (see [Section 3.7.2.4](#)).

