2. CCI [REDACTED]

Protocol 156-13-211

3. Record vital signs (post-void weight, seated heart rate, and calibrated blood pressure measurement).
4. Collect blood for serum chemistry, serum creatinine, ALT, serum sodium and hematology and coagulation.

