3.7.2.3 Physical Examination and Vital Signs

A full physical examination will be performed and documented at the screening visit although this may be combined with the last visit from the previous trial. At other visits, an optional directed physical examination may be performed to focus on ADPKD-related signs and symptoms. In some geographic regions, more frequent subject visits may be the norm; however vital signs and clinically significant physical findings will be recorded as an unscheduled visit in the electronic case report form (eCRF) as applicable. Any changes in medication or AEs will be recorded in the eCRF.

Height will be measured only at screening. Body weight will be taken post-void. It is preferable to use the same scale for each measurement. Clinic scales should be calibrated at least yearly. The investigator or his/her appointed designee is primarily responsible to perform the physical examination. If the appointed designee is to perform the physical examination, he/she must be permitted to do so by local regulations and his/her name must be included on any globally and locally required documents (eg, individual must be added for all sites on a US Food and Drug Administration (FDA) Form 1572, where local regulations allow, while local regulations determine their being named in the ICF). Whenever possible, the same individual should perform all physical examinations. Any undesirable condition present at a post-treatment physical examination that was not present at the baseline examination should be documented as an AE and followed to a satisfactory conclusion.

Vital sign data, including seated blood pressure, heart rate, height, and weight will be taken at the visits identified in the Schedule of Assessments ([Table 3.7-1](#)).

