3.4 Trial Visit Window

Due to the extended duration of the study, the individual patient data will be summarized by period.

For assessments recorded at clinic visits, except for the hepatic monitoring for the subjects from Trial 156-08-271, data will be derived by mapping the study day of the assessment into corresponding time windows as specified in [Table 3.4.1](#). Study day is calculated as: date of assessment - date of enrollment (ie, screening or baseline date) + 1. If there are multiple observations within the same study time window, only the last observation within that study week will be used for the summary tables. The time window mapping rules are applicable to all post first dose safety and efficacy assessments (unless otherwise stated) that are assessed at the scheduled or unscheduled visits (excluding early termination visits/end of treatment visits).

Table 3.4.1 Mapping of clinic visit assessments to study month (except for hepatic monitoring for Subjects from Trial 156-08-271)

Study Month	Study Day Interval
Monthly Visit	
Month 1	2 – 46
Month 2	47 – 76
Month 3	77 – 107
Month 4	108 – 137
Month 5	138 – 168
Month 6	169 – 198
Month 7	199 – 229
Month 8	230 – 259
Month 9	260 – 290
Month 10	291 – 320
Month 11	321 – 351
Month 11	352 – 381
Month 13	382 – 412
Month 14	413 – 442

Protocol 156-13-211

Month 15	443 – 473
Month 16	474 – 503
Month 17	504 – 534
Month 18	535 – 595
Every 3 Months	
Month 21	596 – 686
Month 24	687 – 778
Month 27	779 – 869
Month 30	870 – 961
Month 33	962 – 1052
Month 36	1053 – 1144
Month 39	1145 – 1235
Month 42	1236 – 1327
Month 45	1328 – 1418
Month 48	1419 – 1510
Month 51	1511 – 1601
...	...

Note: Early Termination/End of Treatment (\pm 7 days)

Once Trial 156-13-210 unblinding occurs, it can be determined which subjects received tolvaptan in Trial 156-13-210. These subjects may have their trial visits/hepatic transaminase monitoring changed to every 3 months sooner as their previous tolvaptan exposure in Trial 156-13-210 can count towards the 18-month threshold.

For assessments for hepatic monitoring recorded at clinic visits, for the subjects from Trial 156-08-271, data will be derived by mapping the study day of the assessment into corresponding time windows as specified in [Table 3.4.2](#).

Study Month	Study Day Interval
Every 3 Months (\pm 45 days)	
Month 3	2 – 137
Month 6	138 – 229
Month 9	230 – 320
Month 12	321 – 412
Month 15	413 – 503
Month 18	504 – 595
Month 21	596 – 686
Month 24	687 – 778
Month 27	779 – 869

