8.3 Vital Signs Data

Summary statistics for changes from baseline in vital signs and potentially clinically significant results in vital signs will be summarized by parent study (and prior treatment).

Incidence of potentially clinically significant vital sign results will be summarized by parent study (and prior treatment). Criteria of potentially clinically significant vital sign abnormalities are provided in [Appendix 2](#).

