8.4 Serum Sodium

The following will be summarized by parent study (and prior treatment):

- Serum sodium excursions above 145, 150, or 155 mmol/L or below 136, 130, or 125 mmol/L

Interruptions of protocol-specified therapies for hypernatremia or hyponatremia.

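### SAP 3.4's last-observation-per-window default is not limited to by-visit tables; read literally, it can drop abnormal values from vital-sign incidences and, unless unseen laboratory text says otherwise, from sodium and liver-threshold counts

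*SAP*

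**What the plan says.** - **SAP 3.4, selection rule.** Assessments are assigned to windows by study day. If a window holds more than one observation, "only the last observation within that study week will be used for the summary tables". The mapping covers every safety assessment after the first dose, save where the SAP says otherwise, that is "assessed at the scheduled or unscheduled visits (excluding early termination visits/end of treatment visits").
- **SAP 8.3.** "Incidence of potentially clinically significant vital sign results will be summarized by parent study (and prior treatment)", using the Appendix 2 criteria. No rule for choosing among values is given.
- **SAP 8.4.** The item summarised is "Serum sodium excursions above 145, 150, or 155 mmol/L or below 136, 130, or 125 mmol/L". Again no selection rule is given.
- **SAP 8.** Transaminase elevations are to be tabulated by multiple of ULN (2, 3, 5 and 10), with times to onset, peak and offset. Summary statistics are said to rest on all available data.
- **SAP laboratory section.** The available text breaks off in 8.1.2 and resumes at the Hy's Law paragraph, which promises an incidence table and a listing. How that section opens cannot be read.
- **Protocol 3.1.** On leaving monthly monitoring: "After that, following the approval of the medical monitor, hepatic monitoring will take place every 3 months".
- **Protocol 3.7.1.3 and 3.7.1.5.** At monthly visits: "Collect blood for central laboratory assessments for serum sodium, serum creatinine, and ALT". At early termination/end of treatment (ET/EoTx): "Collect blood for serum chemistry, serum creatinine, ALT, serum sodium and hematology and coagulation". Vital signs are taken at both.
- **Protocol 3.7.2.3.** In regions where extra visits are customary, "vital signs and clinically significant physical findings will be recorded as an unscheduled visit".
- **Protocol 3.7.2.4.1.** A transaminase or bilirubin above 2xULN calls for a retest within 72 hours, then at least weekly tests in the first month while values stay abnormal.

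**The concern.** An excursion count, a threshold frequency and a potentially clinically significant incidence all ask whether a subject ever crossed a limit. A last-value rule answers a different question: where the subject stood at the end of the window. Because the rule is written as a default, an exception has to be stated, and the two sections that can be read in full state none.

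The error can go only one way. A count based on some of the values cannot exceed a count based on all of them, so following the rule can only lower these incidences. The loss falls on the subjects measured most often, who include those retested because a value was abnormal. Long-term safety is the trial's only stated objective, and these tables are among its main results.

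**Working it through.** The plan gives no figure on this point to reproduce. The check uses the windows in SAP Tables 3.4.1 and 3.4.2 and the visit rules in the protocol.

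**1. Window length** = last day - first day + 1.

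| Window | Days | Length |
|---|---|---|
| Table 3.4.1, Month 1 | 2-46 | 45 |
| Table 3.4.1, Months 2-17 | e.g. 47-76, 77-107 | 30-31 |
| Table 3.4.1, Month 18 | 535-595 | 61 |
| Table 3.4.1, Month 21 | 596-686 | 91 |
| Table 3.4.1, Month 24 | 687-778 | 92 |
| Table 3.4.2, Month 3 (hepatic, Trial 156-08-271) | 2-137 | 136 |

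**2. Scheduled visits per window.** Nominal day of monthly visit k = 1 + 30.4375 x k.

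- Up to the Month 17 window, monthly visits fall one per window, so scheduled sodium and vital signs lose nothing.
- Days 535-595: Month 18 = Day 549 and Month 19 = Day 579. That is 2 visits with 1 used.
- Days 596-686: Months 20, 21 and 22 = Days 610, 640 and 671. That is 3 visits with 1 used.
- Days 687-778: Months 23, 24 and 25 = Days 701, 732 and 762. That is 3 visits with 1 used.

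Each of these visits stays in its window when moved by 7 days either way. If a single excursion is equally likely at each visit, it is missed with probability 1/2 in the Month 18 window and 2/3 in the Month 21 and 24 windows. This applies only to subjects still on monthly visits. A subject on 3-monthly visits has one scheduled visit per window (Days 549, 640, 732).

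**3. Repeats after an abnormal liver test.** Assume the abnormal value is equally likely on any day of a window of length L and the retest comes 3 days later. The retest then falls in the same window with probability (L - 3)/L:

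- 27/30 = 90%
- 42/45 = 93%
- 58/61 = 95%
- 88/91 = 97%
- 133/136 = 98%

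If the rule governs the liver tables and the retest is entered, the triggering value is nearly always superseded.

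**4. ALT illustration, on assumed values only.** Assume a 6xULN peak at the trigger or at the retest 3 days later, decay towards 1xULN with a half-life of 7, 14 or 28 days, weekly tests after the retest, and all results entered. Then:

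value kept = 1 + 5 x 2^(-lag/half-life), where lag = days from peak to last test in the window.

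| Tests | Lag | 7 d | 14 d | 28 d |
|---|---|---|---|---|
| Days 92, 95, 102 (31-day window), peak at trigger | 10 | 2.86 | 4.05 | 4.90 |
| Same, peak at retest | 7 | 3.50 | 4.54 | 5.20 |
| Day 641, retest 644, last weekly test 672 (91-day window), peak at trigger | 31 | 1.23 | 2.08 | 3.32 |
| Same, peak at retest | 28 | 1.31 | 2.25 | 3.50 |

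If 'study week' is taken at its word, trigger and retest share a week (week 14 or week 92) and the retest is kept. With the peak at the trigger (lag 3) that gives 4.71, 5.31 or 5.64xULN; with the peak at the retest it gives 6.00. Nothing is lost if ALT is still rising at the last test in the window.

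**The case against.** The strongest reply is that SAP 3.4 is a visit-window section. It opens by saying data are summarised by period, so the last-observation sentence merely chooses the value for each period cell. The tables in 8.3 and 8.4 are described by parent study and prior treatment, with no period dimension, and a subject-level count needs no window. SAP 8 also speaks of all available data and asks for time to peak and response to re-challenge, which one value per 61- to 92-day window could not support. This reading is plausible and may well be the intent. It is not written down, however. The sentence covers the summary tables without limit, and the all-available-data wording names no selection rule. Relying on intent leaves the choice to the programmer.

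Sodium is a laboratory test, so the unseen text may contain a rule that covers it as well as ALT/AST. That stands. Only the vital-sign limb is free of the condition.

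The consequence for liver cases is limited, and that stands too. The rule affects summary tables only, and Hy's cases also get a listing. ALT or AST at or above 3xULN from normal screening levels requires a liver eCRF and review by the hepatic adjudication committee. Laboratory changes judged clinically significant are recorded as adverse events. The liver eCRF and committee do not cover sodium or vital signs, and none of these routes corrects an understated incidence table.

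A reader might infer that ET/EoTx values are lost. The documents do not support that. The parenthesis takes those visits out of the window mapping, and with it the last-observation rule; it does not discard their values. What is missing is a statement that they enter the 8.3 and 8.4 counts.

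**Conclusion.** The concern holds in a limited form. The default in SAP 3.4 is not confined to by-visit tables, and SAP 8.3 and 8.4 contain no exception. Followed literally, it undercounts potentially clinically significant vital signs and, unless the unseen laboratory text provides otherwise, sodium excursions, transaminase thresholds and Hy's criteria.

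The firm figures are 1 of 2 scheduled values unused in Days 535-595 and 2 of 3 in Days 596-686, for a subject still on monthly visits after Month 18. The protocol's normal course is 3-monthly visits by then, and the share of exceptions is not given, so no trial-wide loss can be computed. Before that point the loss comes from unscheduled repeats only.

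It would go too far to conclude that the tables will be wrong, or that ALT peaks will shrink by the amounts illustrated. Those amounts depend on the assumed peak, half-life and entry of retests. The largest fall after Month 18, where Protocol 2.1 reports new elevations at a rate similar to placebo.

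**What to change.** In SAP 3.4, limit the last-observation rule to by-visit means and changes from baseline, and replace 'study week' with 'window'. Say also whether the rule extends to Table 3.4.2 and whether local laboratory retests enter the tables.

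In SAP 8, 8.3, 8.4 and the laboratory section, state that potentially clinically significant incidences, sodium excursions, transaminase-threshold frequencies and Hy's criteria use the worst of all post-first-dose values, scheduled or unscheduled, with ET/EoTx and follow-up values expressly included. State that time to onset, peak and offset use every dated result. If the laboratory section already says this, a cross-reference from 3.4 and 8.4 is enough for those items, and only 8.3 needs new text.

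The cost is SAP wording and programming. No new data are needed, and visit schedules and clinical rules are unaffected.

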5. CCI [REDACTED]
6. CCI [REDACTED]
7. Collect urine for urinalysis, urine osmolality (optional), urine specific gravity.
8. Perform urine pregnancy test on WOCBP. If positive, a follow-up serum test will be performed.
9. An optional directed physical examination may be performed to focus on PKD-related signs and symptoms.
10. Assess tolerability/dosing review of IMP.
11. Enter subject status in IRT, including any dose-regimen changes since the previous entry.
12. Collect and reconcile returned IMP; assess compliance.
13. Update concomitant medications.
14. Assess AEs.

3.7.1.6 7-day Follow-up Visit (+ 7 days)

1. Record vital signs (post-void weight, seated heart rate, and calibrated blood pressure measurement).
2. Collect blood for serum creatinine and ALT.

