3.7.2.2 Clinical Laboratory Assessments

Central laboratory non-fasting serum laboratory tests will be performed. It is preferable to collect the clinical laboratory samples from each subject at a consistent time of day throughout the trial, and to recommend that the subject have a similar diet, avoiding variation in protein intake (especially cooked meat protein) and exercise pattern in order to reduce variability in the samples over time.

CCI
 [REDACTED]
 [REDACTED]
 [REDACTED]
 [REDACTED]
 [REDACTED]
 [REDACTED]
 [REDACTED]
 [REDACTED]
 [REDACTED]

A list of the specific clinical laboratory assessments is presented in [Table 3.7.2.2-1](#).

Clinical laboratory samples will be collected and sent to the central laboratory at the following time points:

Screening: Hematology and coagulation panel, serum chemistry panel, liver function panel (AST, ALT, alkaline phosphatase, bilirubin direct [BT]) serum sodium, serum creatinine, urinalysis panel, urine osmolality (optional), urine specific gravity, urine pregnancy test (WOCBP) and hepatitis (optional).

Monthly visits (± 7 days): ALT (for the first 18 months for subjects enrolled from other tolvaptan ADPKD trials and Trial 156-13-210 while trial remains blinded), serum sodium, and serum creatinine (all subjects), urinalysis, urine osmolality (optional), urine specific gravity, and urine pregnancy test (every 3 months in WOCBP). CCI
 [REDACTED]

Every 3 months: (± 14 days): ALT (after 18 months of treatment for subjects enrolled from other ADPKD tolvaptan trials, or from Trial 156-13-210 after the trial is unblinded, and for subjects enrolled from Trial 156-08-271), serum sodium and serum creatinine,

Protocol 156-13-211

urinalysis panel, urine pregnancy test (WOCBP), urine osmolality (optional), and urine specific gravity. P^{CCI} [REDACTED]

Early Termination/EoTx (+ 7 days): Serum chemistry panel, hematology and coagulation panel, ALT, serum sodium and serum creatinine, ^{CCI} [REDACTED], urinalysis panel, urine pregnancy test (WOCBP), urine osmolality (optional), and urine specific gravity.

7-day Follow-up visit (+ 7 days): ALT, serum creatinine, and urine pregnancy test (WOCBP).

Table 3.7.2.2-1 Clinical Laboratory Assessments	

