INR	Increase	ULN	>ULN - 1.5xULN	>1.5xULN - 2xULN	>2xULN	
Sodium (mg/dL)	Increase	≤ 145	146 - 150	151 - 155	156 - 160	>160
Triglycerides (mg/dL)	Increase	ULN	>ULN - 2.5xULN	>2.5xULN - 5xULN	>5xULN - 6xULN	>6xULN
Urea Nitrogen (mg/dL)	Increase	≤ 22	>22-26	>26-31	>31	
White Blood Count (Thous/ μ L)	Increase	≤ 10.799	>10.799-15	>15-20	>20-25	>25

* Baseline creatinine is expected to be elevated in this population. Average baseline (AB) is equal to the mean baseline value collected during screening period.

During treatment with tolvaptan, serum creatinine is expected to increase by approximately 5-10%. When these tables are generated during the double-blind conduct, the post-randomization comparisons will be made to the post-randomization (PR) value which equals the value collected post-randomization at Month 1 visit. After data-base lock, final reporting of unblinded tables and listings, APR should be changed to the highest value obtained during the run-in period matching the subject's assigned treatment, ie, either placebo or tolvaptan run-in periods.

Protocol 156-13-211

(Laboratory Test Abnormalities due to Test Value Decrease)

Test	Abnor- mality	Test Result Grade				
		-4	-3	-2	-1	0
Glucose (mg/dL)	Decrease	<30	30-<40	40-<55	55-<65	≥65
Hemoglobin (g/dL)	Decrease	<6.5	6.5-<8	8-<10	10-<LLN	LLN
Lymphocytes, Absolute (Thous/μL)	Decrease	<0.2	0.2-<0.5	0.5-<0.8	0.8-<LLN	LLN
Neutrophils, Absolute (Thous/μL)	Decrease	<0.5	0.5-<1	1-<1.5	1.5-<LLN	LLN
Platelet Count (Thous/μL)	Decrease	<25	25-<50	50-<75	75-<LLN	LLN
Potassium (mEq/L)	Decrease	<2.5	2.5-<3		3-<LLN	LLN
Sodium (mg/dL)	Decrease	<120	120-124	125-129	130-135	≥136
White Blood Count (Thous/μL)	Decrease	<1	1-<1.5	1.5-<2.5	2.5-<3.501	≥3.501

Protocol 156-13-211

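### SAP 3.4 leaves the end-of-treatment visit out of the study-month rows but lets in the off-drug 7-day follow-up visit

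*SAP*

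**What the plan says.** SAP 3.4 (Trial Visit Window) assigns each assessment to a study month by study day. On scope it says: "The time window mapping rules are applicable to all post first dose safety and efficacy assessments (unless otherwise stated". The rule covers assessments "that are assessed at the scheduled or unscheduled visits (excluding early termination visits/end of treatment visits". When several values fall in one window, "only the last observation within that study week will be used for the summary tables".

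Protocol 3.7.1.6 schedules a follow-up visit 7 days after treatment, with a window of +7 days. At that visit staff are to "Collect blood for serum creatinine and ALT" and to "Record vital signs (post-void weight, seated heart rate, and calibrated blood pressure measurement". Protocol 3.7.2.2 gives the same laboratory list for this visit: "ALT, serum creatinine, and urine pregnancy test (WOCBP". Sodium, hematology and the chemistry panel are not on it.

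SAP Section 8 summarizes safety variables from all available values, and SAP 8.3 (Vital Signs Data) sets no on-treatment limit. SAP 6.4 and Protocol 3.8.3 and 3.12 also prefer that subjects who stop tolvaptan stay on scheduled visits, whereas Protocol 3.7.5 says they end participation.

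**The concern.** The rule drops the visit closest to the end of dosing and keeps the one visit that is off drug by design. Because the follow-up is later, the last-observation rule then selects it. A reader of a study-month table would take the row to describe subjects on tolvaptan at that time, yet some of its values come from after tolvaptan was stopped.

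This matters because the trial's only objective is to describe long-term safety, so these descriptive tables are its main product. For creatinine the SAP itself expects a difference between on and off drug (Appendix 1 footnote): "During treatment with tolvaptan, serum creatinine is expected to increase by approximately 5-10" percent.

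**Working it through.** **Inputs.** Window bounds come from SAP Tables 3.4.1 and 3.4.2. Days 352-381, labelled Month 11 a second time, are treated as a separate window. Follow-up at f = 7 to 14 days after the last dose is from Protocol 3.7.1.6. The creatinine rise of 5-10% on drug is from SAP Appendix 1. The plan states no figure on this point to reproduce.

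**1. Does the follow-up value pass the rule?** It is post first dose, it comes from a scheduled visit, and it is not an early termination or end-of-treatment visit. So it is mapped. No regular visit is planned after it, so it is normally the last eligible value in its window. Scheduled values from subjects who remain in the trial off drug pass in the same way.

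**2. Which row does it enter?** Assume the stop day is uniform over D days divided into n windows. Stops in the last f days of a window push the follow-up into the next one, so

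share in the same window = 1 − n × f / D.

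| Windows | D | n | f = 7 | f = 10 | f = 14 |
|---|---|---|---|---|---|
| Monthly, days 2-534 | 533 | 17 | 77.7% | 68.1% | 55.3% |
| 3-monthly, days 596-1510 | 915 | 10 | 92.3% | 89.1% | 84.7% |
| Hepatic windows for Trial 156-08-271, days 2-869 | 868 | 9 | 92.7% | 89.6% | 85.5% |

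For example, monthly at f = 14: 1 − 17 × 14 / 533 = 0.553.

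**3. If dosing ends at a planned monthly visit.** The upper bound for Months 1-17 is 30.5 × (month + 0.5), and an on-time visit falls near day 30.5 × month + 1. For Month 2 the visit is day 62, the follow-up is days 69-76 and the window is days 47-76. All of it fits, with no day to spare at +14. If the visit is 7 days late (day 69) and follow-up is at +14 (day 83), the value falls in Month 3.

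**4. Does it displace an on-drug value or stand alone?** With on-time visits and a uniform stop day over days 32-534, the follow-up overwrites the last regular-visit value in about 25% of cases at f = 7 and 1% at f = 14. Otherwise it is the only planned value in its window, since any end-of-treatment value has been left out.

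**5. Size for creatinine.** If a share p of a row's values is off drug and the rise r has fully reversed (an assumption), the row shows r × (1 − p).

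- p = 2%: 5 × 0.98 = 4.9%; 10 × 0.98 = 9.8%.
- p = 10%: 5 × 0.90 = 4.5%; 10 × 0.90 = 9.0%.
- p = 100%: 0%.

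**6. On-drug baseline.** Subjects from Trial 156-08-271 keep their last dose, and their final visit there may serve as baseline here. If they are still dosing at that visit (an assumption), an off-drug value reads as a fall of 1 − 1/1.05 = 4.8% to 1 − 1/1.10 = 9.1%.

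**The case against.** The strongest replies are these.

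- **The rows are headed Study Month, and the SAP never calls them on-treatment.** This stands. Summaries use all available values and nothing is tested, so no error rate is at risk. It limits the severity; the rows still mix on-drug and off-drug values without saying so.
- **A reader might infer that every leaver's last month on drug is filled by an off-drug value.** The documents do not support that. Subjects who miss the follow-up contribute nothing. Under a uniform stop day, about 22-45% of follow-ups in monthly windows and 8-15% in 3-monthly windows fall in the next row. That next row still receives an off-drug value.
- **A reader might infer that ALT signals are diluted toward normal.** This is unsupported. Protocol 2.1 puts reversal of liver tests at about 4 months after stopping in subjects who met Hy's laboratory criteria, so ALT at 7-14 days may still be raised. The listed liver outcomes (threshold frequency, onset, peak, offset, de-challenge) are not monthly means, and some of them need post-drug values.
- **The laboratory rules may say otherwise.** The end of SAP 8.1.2 and the start of the laboratory section are missing from the public text, and the mapping rule allows exceptions. This stands for ALT and creatinine. It does not reach weight, heart rate and blood pressure, because SAP 8.3 is visible and states no limit.
- **End-of-treatment values may be tabulated separately, and may not be on drug.** Both are possible. The notes under the two window tables mention the visit, but SAP 3.4 does not say how its values are shown. Its own +7 day window means an on-drug sample is not assured.
- **The creatinine figure is borrowed.** The footnote giving 5-10% speaks of double-blind conduct and run-in periods, which this trial lacks. It is used here only as the SAP's own indication of size.

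**Conclusion.** The point holds as a moderate defect in a stated rule. Followed literally, SAP 3.4 puts one off-drug set of vital signs into a study-month row for each subject who attends follow-up, completers included. It does the same for ALT and creatinine, subject to the unseen laboratory text. Sodium, hematology and the chemistry panel are unaffected by the follow-up visit.

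The size depends on the off-drug share of a row. At 2-10% the change in mean creatinine is at most one percentage point. It grows in late rows if few subjects remain and many of them are leaving. A reader might take the bias to run always toward no effect. It need not: with an on-drug baseline it would appear as a spurious fall. These sizes rest on full reversal within 7-14 days, and the window shares on a uniform stop day; neither is stated in the documents.

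**What to change.** In SAP 3.4:

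1. Limit study-month mapping to assessments on or before a stated cut-off tied to the last IMP dose date, for example last dose + 1 day.
2. Map an early termination or end-of-treatment value that meets this limit to its window, and also show that visit in its own row. The separate row also gives a place to hematology and the chemistry panel, whose only planned post-baseline sample is at that visit.
3. Report the 7-day follow-up and all later off-IMP values in a separate post-treatment row.
4. Say that the cut-off applies to the study-month rows only, so that the offset and de-challenge summaries keep their post-drug values.
5. Reconcile the end-of-treatment window: ± 7 days in the SAP table notes, + 7 days in the protocol.

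Protocol 3.7.5 should also be reconciled with 3.8.3 and 3.12 on whether subjects who stop IMP stay in the trial. The SAP rule above works either way.

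The cost is a few sentences and a programming flag built from the last dose date. The downside is slightly fewer values in the last windows.
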